In a recently completed study at NYSPI, patients were randomized to RUL ECT at 6 times initial seizure threshold or BL ECT at 2.5 times initials seizure threshold. In addition, the groups were also randomized to use of a traditional wide pulse width (1.5 ms) or use of an ultra-brief pulse width (0.3 ms) ([name], 2004a, [name] et al., 2008). There were marked advantages for the ultra-brief pulse width in acute, short-term and long-term cognitive outcomes. For example, a normal comparison group, comprised of individuals with negative psychiatric and neurological histories, matched to the patient sample in age, gender, education, and verbal IQ, was administered the same neuropsychological battery at the same time interval as given to patients. The Columbia University Autobiographical Memory Interview (AMI) is extremely sensitive to the amnestic effects of ECT in producing forgetting for past autobiographical events (McElhiney et al., 1995, [name] et al., 1993, Sabin et al., 1995b, Lisanby and [name], 2000, [name] et al., 2000b). Patients treated with RUL ultrabrief ECT did not differ from the normal comparison group in amnesia scores when tested a few days (mean=4 days) following the ECT course. This outcome was striking. In contrast, the BL ultra-brief group had a significant deficit, but was superior to the RUL wide pulse width group, who in turn were superior to the BL wide pulse width group. At the short-term time point, the deficit in the BL wide pulse width group was equivalent to a reduction (relative to controls and RUL ultra-brief ECT) of approximately 1.5 SD. This pattern was also maintained at reassessment 6 months following the end of ECT. Thus, these new findings suggest that some forms of ECT result in persistent impairment, especially in the area of retrograde amnesia, but that some innovations in ECT technique may minimize such deficits. The use of ultra-brief stimulation and the right unilateral electrode placement appears to retain efficacy and yet lead to the least degree of impairment. The ultimate goal of the research proposed in this application is to determine whether an additional modification, the use of FEAST to produce greater focality of stimulation, is of further benefit in protecting patient from adverse cognitive effects.

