It has long been thought that age is a risk factor for greater adverse cognitive effects, although the evidence for this has been relatively weak (Zervas et al., 1993, Stoudemire et al., 1991, Mulsant et al., 1991-) [see [name] (2004b) for a review]. In the study of ECT in community settings (Prudic et al., 2004a, [name] et al., 2007), there were two individual difference factors that were strongly related to short- and long-term cognitive outcomes. Older patients generally showed greater deficits and those with higher premorbid IQ [assessed with the National Adult Reading Test; (Crawford et al., 1991)] had smaller deficits. These findings confirmed the suggestion that there is great vulnerability to adverse cognitive effects with advanced age, and raise the possibility that higher premorbid IQ has protective effects, perhaps through a cognitive reserve mechanism, as seen in neurological disorders (Stern, 2002, Legendre et al., 2003).

The fourth central feature is that *ECT results in highly characteristic cognitive changes*. Across psychiatric disorders and prior to receiving ECT, many patients have deficits in attention and concentration that limit their capacity to learn new information (immediate memory) (Byrne, 1977, Pogue-Geile and Oltmanns, 1980, Cornblatt et al., 1984, [name] and Steif, 1988, Zakzanis et al., 1998, Majer et al., 2004). For example, patients with severe psychopathology often have deficient recall of

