2. Past and Current Medication and ECT History (Antidepressant Treatment History Form) ([name], 2001, [name] et al., 1990b)
3. Clinical Global Impression: Severity & Improvement (CGI:S, CGI:I) (Guy, 1976)
4. Global Assessment Scale (GAS) (Endicott and Spitzer, 1978)
5. Hamilton Rating Scale for Depression (HRSD) (Hamilton, 1967)
6. Montgomery-Åsberg Depression Rating Scale (MADRS) (Montgomery and Asberg, 1979)
7. Inventory for Depressive Symptoms (IDS-SR) (Rush et al., 1985)
8. Medical Outcomes Study - SF36 (MOS-SF36) (Wells et al., 1992, McHorney et al., 1993)
9. Demographics (age, education, race, marital status) and handedness

Baseline Measures in Cognitive Battery

Global Cognitive Function

1. Modified Mini-Mental State Exam (mMMS) (Stern et al., 1987, Mayeux et al., 1981)

Retrograde Memory

1. Columbia University Autobiographical Memory Interview – Short Form (AMI) (McElhiney et al., 2001, McElhiney et al., 1995, Sabin et al., 1995b, [name] et al., 1993, [name] et al., 2000b, [name], 2014b)

Anterograde Memory

- I. Buschke Selective Reminding Test (BSRT)

Patient Attitudes

1. ECT Attitude Interview (Berman et al., 2008, Brakemeier et al., 2011b)

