The primary analysis for Hypothesis 4 will use all available HRSD₂₄ data (i.e., the intent-to-treat data) from the FEAST and UB RUL ECT samples. A random regression model will be used to examine the relationship between HRSD₂₄ scores and treatment group. Time will be the within-subjects repeated measures factor, site and treatment group the between-subjects factors, with medication-resistance classification and baseline HRSD₂₄ serving as covariates. All interactions with time will be modeled. In secondary analyses, we will also include age, gender, age-at-onset of illness, and duration of current episode as covariates, if pre-screening indicates utility. We will investigate whether HRSD₂₄ scores are linear in time or quadratic, cubic, or piece-wise linear (e.g., hockey-stick shaped). Indeed, in a study comparing several different statistical methods in their sensitivity to ECT treatment groups differences in rate of clinical improvement, we found that the HRSD₂₄ scores over time were frequently nonlinear (Nobler et al., 1997a). The type of analysis conducted on HRSD₂₄ scores will be repeated for secondary analyses with the MADRS, IDS-SR, and CGI-S.

FEAST and UB RUL ECT will also be compared in the categorical outcomes of final remission status (HRSD₂₄ of 10 or less at post-treatment) in a secondary analysis to gauge generality of the effect and clinical significance. Nominal logistic regression analysis will be used to compare the treatment groups in covariate-adjusted odds of remission. Remission status will be the dependent variable. The independent variables will be the treatment group indicator, along with site, medication resistance, and baseline HRSD₂₄.

Hypothesis 5. In two primary cognitive measures, orientation recovery time and CUAMI-SF scores, FEAST will have a significant advantage relative to UB RUL ECT.

The cognitive measures were described in Section B.12. Orientation time will be averaged within each patient across all treatments. An ANCOVA will be conducted on these values with Site and Treatment Group as between-subject factors, and age and number of treatments in the average as covariates. A similar ANOVA will be conducted on CUAMI-

SF scores, with Site and Treatment Group as between-subject factors, and age, number of treatments, and baseline CUAMI-SF score as the covariates.

Hypothesis 6. FEAST will have a significant advantage in the subjective global evaluation of the effects of ECT on memory.

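### The Hypothesis 5 memory comparison carries no marker of premorbid ability, although the protocol reports it as related to cognitive outcome and education is already collected

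*Combined protocol and SAP*

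**What the plan says.** Section III.C.5 (Objective Cognitive Side Effects), on the community-settings study, says that "there were two individual difference factors that were strongly related to short- and long-term cognitive outcomes". Older patients had larger deficits, and "those with higher premorbid IQ [assessed with the National Adult Reading Test; (Crawford et al., 1991)] had smaller deficits".

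Section IV.B.15, Hypothesis 5, is a superiority claim: "In two primary cognitive measures, orientation recovery time and CUAMI-SF scores, FEAST will have a significant advantage relative to UB RUL ECT". The CUAMI-SF model has site and treatment group as factors, "and age, number of treatments, and baseline CUAMI-SF score as the covariates". The orientation-time model uses "age and number of treatments in the average as covariates".

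The study overview that opens Section IV matches the comparison group within site on gender, unipolar or bipolar diagnosis, age and baseline modified Mini-Mental State (mMMS) score. Table 3 (Section IV.B.5) records "Demographics (age, education, race, marital status) and handedness"; the battery contains no premorbid IQ test.

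Section IV.B.1 describes an open, non-randomised, unmasked study. Section III.D.2 says that FEAST patients choose FEAST. Under Data Screening, Section IV.B.15 compares the groups on baseline sociodemographic and clinical features at P<0.2 but does not say what follows from a difference. The only rule that brings in extra covariates after pre-screening belongs to the Hypothesis 4 secondary analyses, and education is not among them.

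**The concern.** Of the two patient factors that the protocol reports from the community study, the memory model takes age and leaves out premorbid ability. Randomisation would balance the omitted factor on average. Here the groups form by patient choice on one side and routine scheduling for conventional treatment on the other, so nothing in the design balances it.

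If the groups differ in premorbid ability, the group term in the CUAMI-SF model takes up part of that difference. Baseline CUAMI-SF adjusts for starting level, but the cited finding concerns the size of the deficit after treatment, so this need not remove the problem.

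Section IV.B.5 calls the CUAMI-SF the most critical of the retained cognitive measures. Section IV.B.15 says that the effect sizes will be used to power a later randomised study, so a biased estimate would carry forward.

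**Working it through.** The plan gives no power calculation, standard deviation, effect size or test level for Hypothesis 5, so there is no stated figure to reproduce. The covariate and matching lists were checked against the text; neither contains education or IQ.

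**Inputs**
- From the documents: 40 patients per group.
- Assumed: two-sided 5% test; imbalance d of 0.2-0.5 SD in premorbid IQ, taken here as favouring FEAST; slope b of 0.1-0.4 SD of post-course CUAMI-SF per SD of IQ, given the planned covariates; education-IQ correlation 0.6.

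**Bias and false advantage with no true effect**
- Bias = b × d.
- Standard error of the group difference = √(2/40) = 0.224 SD.
- Chance of a significant result favouring FEAST = 1 − Φ(1.96 − bias/0.224).
- Low end: 0.1 × 0.2 = 0.02 SD; 1 − Φ(1.96 − 0.09) = 3.1%.
- Middle: 0.3 × 0.3 = 0.09 SD; 1 − Φ(1.96 − 0.40) = 6.0%.
- High end: 0.4 × 0.5 = 0.20 SD; 1 − Φ(1.96 − 0.89) = 14.3%.
- Nominal: 2.5%. If the imbalance favours the comparison group, the same bias works against FEAST.

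For scale, 40 per group has 80% power for (1.96 + 0.84) × 0.224 = 0.63 SD, unadjusted.

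**The baseline screen.** P<0.2 needs an observed difference of about 1.28 × 0.224 = 0.29 SD. A true imbalance of 0.2, 0.3 or 0.5 SD would be flagged with probability 36%, 53% or 83%.

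**What adjustment recovers.** The planned ANCOVA was simulated with no true effect (3,000 runs per setting; baseline CUAMI-SF correlated 0.3 with IQ). The entries are the rate of a significant FEAST advantage.

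| d | b | As planned | Plus education | Plus IQ |
|---|---|---|---|---|
| 0.2 | 0.2 | 4.4% | 3.5% | 2.7% |
| 0.3 | 0.4 | 6.1% | 4.7% | 2.4% |
| 0.5 | 0.4 | 10.3% | 6.5% | 2.4% |

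In the last row the bias falls from 0.178 to 0.117 SD with education, a reduction of (0.178 − 0.117)/0.178 = 34%. With IQ it is essentially zero. The simulated 10.3% is below the analytic 14.3% partly because baseline CUAMI-SF absorbs some of the IQ difference.

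**Sensitivity.** If 0.2-0.4 is read as the overall IQ effect and not as the slope given baseline, a separate simulation (1,500 runs per setting) gave 2.5-9.5% false advantages at a baseline-IQ correlation of 0.3. At a correlation of 0.5 it gave 1.1-5.3%, with the bias sometimes running against FEAST.

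**The case against.** The strongest reply is that the size is assumed throughout and may be small. The cohort behind the IQ finding included sine-wave and bilateral ECT. Under ultrabrief right unilateral ECT the protocol expects only slight autobiographical loss (Section IV.B.5), and Section IV.C.3 reports scores indistinguishable from those of healthy participants. With little deficit to modify, the IQ slope could be near the bottom of the assumed range or below it. This stands, and it limits the severity. It also means that a true FEAST benefit has little room, so a small bias could be a sizeable share of any observed difference.

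The plan is also candid. It presents the comparison as rough and non-randomised, ranks side-effect comparisons behind the EEG aim, and looks to a later randomised trial. That is fair, but it does not explain leaving out a covariate already in hand.

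Three stronger readings are tempting, and the documents do not support them.

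- A reader might infer that premorbid IQ is one of only two predictors that matter. That count comes from one cited study. Sections III.C.5 and IV.B.12 also name baseline global cognitive status as a predictor of retrograde amnesia, and the plan matches on it through mMMS.
- A reader might infer that FEAST patients will be better educated, so that the error must favour FEAST. No section says that they differ, and none links education itself to memory loss after ECT. The cited finding concerns IQ measured by a reading test, and the protocol offers a protective effect only as a possibility.
- A reader might take the earlier pulse-width trial as precedent for matching treatment groups on education. There a healthy comparison group was "matched to the patient sample in age, gender, education, and verbal IQ"; the patient groups themselves were randomised.

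**Conclusion.** The gap is real and modest. The CUAMI-SF model and the matching list contain no marker of premorbid ability, in a self-selected comparison whose baseline screen has no stated consequence for Hypothesis 5. The bias could run either way. The range of 0.02-0.20 SD, with false FEAST advantages of about 3-14%, rests wholly on the assumed imbalance, slope and test level. It shrinks if baseline CUAMI-SF and the mMMS matching absorb part of the IQ effect. This does not show that a favourable memory result would be false. It shows that an inexpensive prespecified safeguard is missing. Modest severity, medium confidence.

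**What to change.** In Section IV.B.15, Hypothesis 5, prespecify years of education as an additional covariate in the CUAMI-SF model. Do the same for the mMMS and BSRT group comparisons described in Section IV.B.12. In the Section IV overview, add education to the variables checked for balance within site.

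State plainly that education is an imperfect proxy. At an assumed correlation of 0.6 it removes only about a third of the bias from an imbalance in premorbid IQ.

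The cost is a few sentences in the plan and one degree of freedom per model, with no new assessment. Table 3 lists education without a unit, so the form should record years. The change should be fixed before outcomes are seen, because adding the covariate later in an unmasked study would invite challenge.

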With respect to optimization of treatment, the key issues are the choice of sites for electrode positioning and the dosing strategy. In using the 1.25" diameter anterior electrode (as opposed to a smaller anode), the degree of focality is reduced and this should protect efficacy. We do not have sufficient knowledge of the functional neuroanatomy to justify greater focality (Nobler et al., 1994, Nobler et al., 2001, Seminowicz et al., 2004). Rather, at this stage, the more limited goals are to restrict seizure onset and expression largely to regions in the right prefrontal cortex (PFC), with virtually no stimulation in left PFC or left or right medial temporal lobe (MTL). In positioning the anode in the area of the Fp2 site in the 10/20 International EEG System, current density will peak broadly through the right anterior PFC. Furthermore, we have taken two steps to ensure that FEAST is not under-dosed. EEG seizures without convulsion are very rare with conventional ECT (Boylan et al., 2001), but may be more frequent with FEAST. Research groups differ in whether or not motor manifestations are required in defining the seizure threshold (ST). In this protocol, we will note the intensity level that results in an "EEG only" seizure, but require that EEG seizure manifestations be clear-cut and last at least 15 s to define the ST value used for subsequent dosing. Second, at any point after the fifth treatment, a clinical evaluation team can recommend a dosage increment, up to 9 x ST. Thus, in this first examination of FEAST, to protect efficacy we have deliberately erred on the side of sacrificing the degree of focality, while also allowing some flexibility in dosing. With stimulation at these levels, it is very unlikely that FEAST will be markedly ineffective, unlike low dosage RUL ECT ([name] et al., 1987b, [name] et al., 1993). Rather, to determine whether there is any effect on efficacy, a substantial number of patients will have to be treated in a masked, randomized protocol (which is planned following this study). Our published data (Nahas et al., 2013a) has demonstrated that FEAST has marked antidepressant effects. However, in the absence of a masked, randomized comparison with traditional ECT, equivalence in efficacy is unknown. This study focuses on the mechanistic issue and attempts to demonstrate that seizures induced by FEAST show robust electroencephalographic activity in frontal electrodes, but reduced activity in

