temporal EEG leads. The lesser involvement of medial temporal structures with the seizures induced by FEAST should result, in turn, in lesser amnestic effects, especially for autobiographical information ([name] et al., 2000a). To accomplish this we propose to compare matched groups of patients who have elected to receive FEAST to non-randomized patients received regular treatment with ultrabrief right unilateral (UB RUL) ECT. Since FEAST delivers an ultra-brief stimulus and an identical titration schedule is used in both groups, the only difference in the stimulation given between the groups will be the features unique to FEAST, i.e., the use of unidirectional stimulation and geometry and positioning of the electrodes. As we will carefully evaluate efficacy, this comparison will provide preliminary (but not definitive) data on whether efficacy is equivalent for FEAST relative to traditional ECT.

In summary, we are confident that FEAST does not increase the risks of ECT. It is simply a form of ECT that is more focal and likely more efficient in seizure induction. We have optimized FEAST's potential for being efficacious by limiting its degree of focality and ensuring that markedly suprathreshold electrical dosage can be administered. By using 1.25" diameter electrodes rather than the earlier 3/4" electrodes, we have demonstrated acceptable impedances and have had no instances of skin burns.

D.3 Titrating in the Current Domain

Another innovation was originally examined in this study. This modification was the use of current or pulse amplitude as the basis for titrating electrical dosage to the patient's seizure threshold. As explained below, we no longer use procedures for titrating in the current domain as part of this study. Our original rationale for this approach and the reasons we no longer include it in the procedures are explained below.

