Across the sites 60 patients will be enrolled to achieve 40 FEAST patients who will fully complete this study at the MUSC Institute of Psychiatry, Brain Stimulation Service (BSS) in Charleston, SC, and at GRU in Augusta, GA and Aiken, SC. At both MUSC and GRU, roughly matched 30 patients (each) will also be recruited from those scheduled to receive UB RUL ECT to obtain a cohort of 40 RUL comparison patients. The FEAST and UB RUL ECT groups must meet identical inclusion/exclusion criteria and will undergo identical evaluation procedures. The only difference between the groups will be that one receives FEAST and other UB RUL ECT. The treatment received by the UB RUL ECT group will not be affected by participating in this protocol. This is an open label, non-randomized, non-masked study. Separate consent forms will be used in each group. We are thus asking FDA permission to study 60 patients with FEAST. An additional 60 patients will be studied who receive conventional ECT. Even though they are getting conventional ECT, they are covered by this FDA IDE as their data will be used for comparison purposes with FEAST.

Patients will be selected from those referred for ECT for the treatment of major depressive episode. To verify diagnosis, the SCID-P will be administered to derive DSM-V diagnosis (unipolar or bipolar major depressive episode) and relevant subtypes and specifiers (American Psychiatric Association, 2013).

Inclusion and exclusion criteria are presented in Table 2. Briefly, patients will be between the ages of 18 and 90 years and will provide informed consent. Exclusions include: history of schizophrenia, schizoaffective disorder or any non-mood disorder psychosis, rapid cycling bipolar disorder, central nervous system illness other than conditions associated with psychotropic exposure, alcohol or substance abuse or dependence in the past 3 months, pregnancy, epilepsy, inability to have stable medications, and ECT within the past six months.

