identified for each individual patient ([name] et al., 1994, American Psychiatric Association, 2001). Dosing at subsequent treatments will be substantially above seizure threshold. With traditional ECT and a RUL electrode placement, a dose of at least 6 times the initial seizure threshold (6xST) has been shown to be maximally effective (McCall et al., 2000, [name] et al., 2000b), with lower dosage resulting in reduced efficacy ([name] et al., 1987b, [name] et al., 1993). This is also the case when an ultrabrief stimulus is used with the RUL electrode placement ([name], 2004a, [name] et al., 2008, Loo et al., 2012). Thus, the minimum dosage for FEAST will be approximately 6xST in treatments administered after the first session [see Table 4]. Given insufficient clinical progress after at least 5 treatments, this dosage may be increased to up to approximately 9xST prior terminating use of FEAST. Since the seizure thresholds with an ultrabrief stimulus are very low ([name], 2004a, Loo et al., 2012), and are expected to be lower still with the use of FEAST, the absolute dosage administered will in almost all cases be well below that commonly administered with routine treatment in the community.

The criterion for determining ST will be EEG determined. In the past 28 patients at MUSC we are now sufficiently confident that FEAST seizures can be seen on EEG. We will also record motor movement cessation in the leg that has the BP cuff inflated.

Table 4. Titration and Dosing Schedule

Titration and Dosing Schedule					
Pulse Frequency (Hz)	Pulse Width (ms)	Train Duration (s)	Current (mA)	Total Charge (mC)	Dose Relative to Initial ST
20	0.3	1	800	9.6	
20	0.3	2	800	19.2	
20	0.3	4	800	38.4	
20	0.3	8	800	76.8	
40	0.3	8	800	153.6	
80	0.3	8	800	307.2	
Subsequent Dosing: 6 X ST					
20	0.3	6	800	57.6	6
30	0.3	8	800	115.2	6
60	0.3	8	800	230.4	6
90	0.4	8	800	460.8	6
90	0.5	8	800	576	3.75
Subsequent Dosing: 9 X ST					

30	0.3	6	800	86.4	9
60	0.3	6	800	172.8	9
90	0.3	8	800	345.6	9
90	0.5	8	800	576	7.5

The titration schedule to be used in the study and the prescribed dosing at treatments following the initial titration session are presented in Table 4. The titration schedule starts with a dose of 9.6 mc, which is nearly the lowest ever used in clinical or research use of ECT, reflecting the expectation that seizure thresholds will be very low.

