We do not anticipate that this form of ECT (unidirectional, ultrabrief pulse with spatial targeting) will have an adverse impact on efficacy, although this is not certain. Potential lack of efficacy likely constitutes the most significant risk of FEAST. Precautions have been taken in this protocol to mitigate this risk. First, patients who do show sufficient benefit after 5 treatments may receive a dosage increment, increasing the stimulus dose from 6xST to 9xST. In the community, dosing of UB RUL ST is often 8xST or more (e.g., (Loo et al., 2012)). Second, any patient who completes the research phase as a nonremitter will be offered a course of traditional ECT (UB RUL ECT, high dose RUL or BL ECT). Our preliminary experience in 35 patients clearly indicates that FEAST has potent antidepressant properties. We cannot, however, say with assurance that these properties are equivalent to traditional forms of ECT, without explicit comparison. This study provides important data in this respect, involving the first cotemporaneous comparison of FEAST and UB RUL ECT, albeit in a non-randomized and non-masked fashion. It is anticipated that the findings obtained here will provide the foundation for a subsequent RCT.

The protocol involves monitoring of objective and subjective side effects and includes provision for alternative treatment for patients who do not respond clinically. Although a large number of procedures are conducted, other than ECT, they are all noninvasive. Patients who consent to the protocol have the option of declining participation in specific procedures (e.g., fMRI studies), but can retain participation in the remaining procedures.

Finally, FEAST might present with two theoretical risks: superficial skin burn and intracerebral damage to excessive current density). The use of an electrode with small surface area could increase the impedance in the circuit and result potentially in skin burn or prevent the passage of the stimulus. This theoretical risk is minimized by the fact that the ECT device voltage limits and immediately aborts stimulus delivery when excessive impedance is encountered. In this protocol, we are requesting that the voltage/impedance

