The most important factor determining the safe use of the device is the dosing of the electrical stimulus. Determining the seizure threshold and adjusting the dose relative to this threshold is concerned the most precise method for stimulus delivery in ECT (American Psychiatric Association, 2001). Stimulus dosing based on the empirical titration (method of limits) method is routine practice at the MUSC and the GRU, and was introduced to the field by [name]. The titration schedule specific to the use of FEAST was presented above (Section IV.B.6). An identical titration schedule will be used at first treatment in the UB RUL ECT group. The maximum dosage (charge) to be administered in this protocol with this device is 576 mC (see Table 4 - titration schedule), the same as the maximal output of the US marketed Spectrum 5000Q

D.6 Protection From Excessive Electrical Dosage

The Spectrum 5000Q FEAST device retains all the safety features of the commercial Spectrum 5000Q. These features include internal tests of the integrity of device operation and the accuracy of stimulus output when the device is powered on and following the completion of each treatment. A continuous static impedance measurement is provided, and the device will not arm for stimulus delivery if static impedance is below 100 or above 5,000 ohms. Under situations of inadequate electrode contact (e.g., slippage), the device automatically terminates stimulus delivery when the delivered voltage be would above the cutoff of 400 V. Each of the stimulus parameters is measured during delivery. If any parameter exceeds

specified tolerances, stimulus delivery is automatically terminated. The operator (Study Psychiatrist) can terminate stimulus delivery at any moment by releasing the treatment button.

D.7 Supervision of Patients During Treatment Sessions

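### Hypothesis 5 averages orientation time over all treatments with no rule for modality switches or dose increases, so its group comparison can mix device with modality or dose

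*Combined protocol and SAP*

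**What the plan says.** **On sameness of stimulation.** Section III.D.2 reasons from a shared ultrabrief pulse and a shared titration schedule to the statement that "the only difference in the stimulation given between the groups will be the features unique to FEAST". Section IV.B.1 says "The only difference between the groups will be that one receives FEAST and other UB RUL ECT", and also "The treatment received by the UB RUL ECT group will not be affected by participating in this protocol". Section IV.D.5 specifies what is shared: "An identical titration schedule will be used at first treatment in the UB RUL ECT group".

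**On dose after titration.**
- FEAST: section III.D.2 says that "at any point after the fifth treatment, a clinical evaluation team can recommend a dosage increment, up to 9 x ST". FEAST Stimulus Dosing in section IV.B.6 says "Given insufficient clinical progress after at least 5 treatments, this dosage may be increased to up to approximately 9xST prior terminating use of FEAST". Sections IV.C.2 and IV.C.5 repeat the step from 6xST to 9xST.
- UB RUL: RUL ECT Stimulus Dosing in section IV.B.6 sets 6xST for sessions after the first and leaves other aspects to routine site practice.
- Arm not named: Number of Treatments in section IV.B.6 offers 6xST to 9xST after five treatments without saying to whom. Section IV.B.7 then says the two groups are handled alike apart from listed exceptions, and dose is not among them.

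**On modality.** Section IV.B.7 allows UB RUL patients to change to brief pulse RUL or bilateral ECT when clinically indicated, with no timing. Under Number of Treatments, FEAST non-responders are offered traditional ECT as a second course with its own efficacy evaluation.

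**On analysis.** Under Hypothesis 5, each patient's orientation time is the mean over all treatments. The ANCOVA has site and group as factors, and age and the number of treatments averaged as covariates. Dose multiple, pulse width and modality do not appear.

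**The concern.** Orientation recovery time is one of two primary cognitive measures, and the protocol describes it as responsive to exactly the things that can change during a course. Section IV.B.12 lists electrode placement, waveform and dosage. Section IV.B.5 lists ultrabrief against brief pulse and bilateral against RUL. Sections III.C.5 and IV.C.3 tie cognitive effects to dose above threshold.

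If later sessions differ between groups in modality or dose, a difference in the course-long mean is not a pure device effect. Adjusting for the number of treatments does not repair this, because both changes follow from clinical progress and not from course length as such. Section IV.B.15 says the study's effect sizes will be used to power a later randomized trial, so a distorted estimate would carry forward.

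Hypothesis 1 is untouched, since it uses threshold at the first treatment. Hypothesis 2 (ictal EEG) is touched only if sessions are pooled. Section IV.B.13 allows pooling, and section IV.B.15 does not say which sessions are used.

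**Working it through.** **1. Which sessions enter the average.** The rule covers all treatments. For FEAST, traditional ECT falls in a separate second course. For UB RUL, the switch sits inside the treatment procedures and no sentence ends the index course or drops later sessions. Read literally, brief pulse or bilateral sessions count in the comparator's mean.

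**2. Possible effect of switching (illustration; all three inputs are assumed).** If a share f of UB RUL patients switch, a share s of their sessions follow the switch, and orientation in those sessions takes r times as long, the comparator's mean changes by f × s × (r − 1). Take s = 0.5 (a switch after treatment 5 of 10):
- f = 0.25, r = 1.25: 0.25 × 0.5 × 0.25 = 3.1%
- f = 0.5, r = 2: 0.5 × 0.5 × 1 = 25%

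If these sessions take longer, the change favours FEAST.

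**3. Table 4 reproduced.** Charge = 2 × current × pulse width × frequency × duration (the formula under Table 1). For example, 2 × 0.8 × 0.3 × 30 × 8 = 115.2 mC, and 115.2/19.2 = 6xST. All charges and multiples in Table 4 reproduce. The increase is:
- ST 9.6 to 38.4 mC: 86.4/57.6 = 172.8/115.2 = 345.6/230.4 = 1.5-fold.
- ST 76.8 mC: 576/460.8 = 1.25-fold (to 7.5xST), with the pulse going from 0.4 to 0.5 ms. Section III.C.2 gives ultrabrief as below 0.5 ms.
- ST 153.6 mC: no step is available. Dosing is already 576/153.6 = 3.75xST at 0.5 ms from treatment 2.

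**4. Dose gap at the stated doses.** Count titration as 1xST, treatments 2 to 5 as 6xST, and the rest as 9xST if escalated (ST up to 38.4 mC). The course lengths 6 and 10 are the two minimums under Number of Treatments; 10 is also the pilot median (section III.D.6).

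| Treatments | FEAST, escalated | UB RUL at 6xST | Gap |
|---|---|---|---|
| 6 | (1 + 24 + 9)/6 = 5.67 | (1 + 30)/6 = 5.17 | +0.50 |
| 10 | (1 + 24 + 45)/10 = 7.00 | (1 + 54)/10 = 5.50 | +1.50 |

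With a share p of FEAST patients escalated over T treatments, the group gap is p × 3 × (T − 5)/T. The table is the case p = 1 with full 9xST from treatment 6, so it is an upper bound at each length. A 14-treatment course, the longest in the pilot, would give 3 × 9/14 = +1.93. If both groups have the option and use it equally, the gap is 0.

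**5. Direction.** A higher multiple in FEAST would be expected to lengthen FEAST's orientation time, because sections III.C.5, IV.B.12 and IV.C.3 associate more dose above threshold with worse cognitive effects. The dose part would therefore work against Hypothesis 5. No section gives a 6xST against 9xST contrast in minutes.

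**The case against.** The dose conflict can be seen as mostly silence. The places that tie 9xST to FEAST are about FEAST and do not deny it to UB RUL, and the two that can cover both groups (Number of Treatments and section IV.B.7) are compatible with one shared rule. This stands in part. A shared rule is a fair reading, and it makes the dose gap zero. But no sentence settles it, and the UB RUL dosing paragraph states 6xST with no increase.

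A reader might infer that the comparator is really dosed at 8xST, so that even the sign of the gap is open, because section IV.C.2 says "In the community, dosing of UB RUL ST is often 8xST or more". The documents do not support that for this study. The figure describes community practice, whereas the study's own UB RUL dose is given as 6xST.

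On modality, one can say that Hypothesis 5 compares FEAST with UB RUL ECT, so sessions of another kind are implicitly out, or that a switch is the counterpart of the FEAST second course. Either would be sensible, but neither is written.

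The 0.5 ms setting is disclosed in section IV.B.6, so it is a feature to report and not a hidden discrepancy. Finally, the comparison is non-randomized and unmasked and is described as rough and preliminary. That stands and limits the severity.

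**Conclusion.** The point holds in a limited form. The stated averaging rule admits comparator sessions given after a change of modality. This is the stronger part, because it could favour FEAST. Its size cannot be given: neither the share switched nor the effect in minutes is stated.

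The dose part is weaker. At the stated doses the gap is 0 to +0.50xST over 6 treatments and 0 to +1.50xST over 10, and any effect would run against FEAST. The upper figure should not be read as typical. It needs every FEAST patient escalated to full 9xST from treatment 6. Escalation is meant for insufficient progress, and in patients below 40% improvement treatment may stop from 6 treatments onward.

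A reader might also infer that an advantage for FEAST on Hypothesis 5 could be produced by unequal dosing, or that the hypothesis cannot be tested. The documents support neither. The claim of identical stimulation is simply secured for the titration session and no further. Severity is minor to moderate.

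**What to change.** 1. Define the Hypothesis 5 orientation average as index-modality sessions only (FEAST, or UB RUL before any switch).
2. Pre-specify a sensitivity analysis on treatments 2 to 5 in every patient, and use the same window for the EEG measures if sessions are pooled. A fixed window is preferable to cutting at each patient's dose increase, which would select by response. Section III.C.5 also reports that orientation recovery quickens over a UB RUL course. Flag any patient who switched or received 0.5 ms within the window.
3. Keep the all-session result alongside.
4. Report delivered dose multiple, pulse width, and proportions escalated or switched, by group. The window is dose-matched only if UB RUL was in fact given at 6xST, so this report is needed to interpret it.
5. State once whether UB RUL patients have the 9xST option, and limit the sentence in section III.D.2 accordingly.

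The cost is small. Orientation is already assessed at every session and the EMR software logs the stimulus parameters (sections IV.B.6, IV.B.12 and IV.E.2). The downside is precision. With 4 sessions instead of 10, the session-noise variance of a patient's mean rises by 10/4 = 2.5-fold if sessions are independent. Restricting sessions does nothing for the other primary cognitive measure, the CUAMI-SF, which is taken after the course. For that measure, reporting switches and doses is the only help.
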